#### 8.1.3.4 *Data from biopsies from the polypectomy site (second investigational endoscopy)*

- Date of the endoscopic procedure.
- Type of procedure (sigmoidoscopy or colonoscopy).
- Finding: scar, tattoo, ulcer, polypous remnant, suspicion of residual cancer, no reliable identification of the polypectomy site.
- Number of biopsies.
- Bleeding (immediate, delayed).
- Perforation (immediate, delayed).

- Intervention for complication (endoscopic, angiographic, surgical).
- Impact of complication on scheduled surgical resection: no change, antedation, postponation, cancellation.
- Severity of complication according to the Dutch Society of Gastroenterology.

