## 8.2 Randomization, blinding and treatment allocation

Not applicable

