### 8.4 Withdrawal of individual subjects

Subjects can leave the study at any time for any reason if they wish to do so without any consequences. The investigator can decide to withdraw a subject from the study for urgent medical reasons. Specific criteria for withdrawal are not applicable

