### 8.5 Replacement of individual subjects after withdrawal

The study will continue until the requested amount of subjects is included.

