## **10 Statistical analysis**

All statistical analyses will be done in the Deventer Hospital, with support of the local department of clinical epidemiology ([name]). Final approval will be obtained from the department of biostatistics and epidemiology at the Erasmus Medical Center ([name]). In principle, sensitivity will be calculated by dividing the number of patients with positive biopsies by the number of patients with tumor in the bowel wall and / or resected lymph nodes. Separate analysis will be done for bowel wall affection (as opposed to lymphatic spread) only.

The above-mentioned factors of potential influence will be studied on associations with the presence or absence of tumor in the bowel wall and / or resected lymph nodes. This will be done by using an independent samples *t*-test in the case of continuous normally distributed variables; by nonparametric test (e.g. Mann-Whitney U-test) in case of non-normally distributed ordinal variables; by Chi-Square statistics in case of categorical variables and by multiple logistic regression to investigate multiple associations.

Missing data will be dismissed from the analysis: the main issue is, whether there are preoperative biopsies and a resection specimen. If one of both fails, the loss will be compensated by the inclusion of another patient, as long as the number of evaluable patients is not reached.

NL51461.078.15 / NCT02328664 Scar biopsies after malignant colorectal polypectomy of uncertain radicality

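### Dropping and replacing every patient without biopsies or a specimen can inflate the estimated sensitivity, and Section 10 has no analysis that would show it

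*Protocol*

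**What the plan says.** Section 10 fixes the rule: "Missing data will be dismissed from the analysis: the main issue is, whether there are preoperative biopsies and a resection specimen". It then adds replacement: "If one of both fails, the loss will be compensated by the inclusion of another patient". This goes on until enough evaluable patients have been reached. Section 8.5 points the same way: "The study will continue until the requested amount of subjects is included".

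The primary estimate comes from "dividing the number of patients with positive biopsies by the number of patients with tumor in the bowel wall and / or resected lymph nodes", so a patient without a specimen cannot enter the denominator. Under the missing-data rule, neither can a patient without biopsies.

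The protocol foresees both kinds of loss. Section 8.1.3.4 lists "no reliable identification of the polypectomy site" among the second-look findings. Section 8.4 states: "Subjects can leave the study at any time for any reason if they wish to do so". Section 8.6 gives withdrawn patients no study follow-up, so their tumor status is not established in any other way. No section says how an attempted second look without a biopsy counts, or how patients without resection are handled beyond being replaced.

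**The concern.** Replacement restores the number of evaluable patients. It does not make them representative of those lost. Two losses could be selective.

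(a) **No biopsy obtained.** The second look was attempted, no tissue was obtained, and the specimen later shows tumor. The second look did not detect that tumor, yet the patient is removed rather than counted against the procedure.

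(b) **No resection.** Section 8.3.1 allows up to four weeks between biopsies and surgery. If a reassuring biopsy makes patients or physicians more likely to forgo resection, biopsy-negative patients go unverified more often and their false negatives disappear.

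The null and alternative in Section 4.4 are only 5 percentage points apart (0.90 and 0.95), so small selective losses can change the conclusion. That conclusion is meant to inform whether rescue surgery can be omitted.

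**Working it through.** **Inputs from the protocol (Section 4.4).** Null sensitivity 0.90, alternative 0.95, alpha 0.05, power 0.80; 194 patients with residual tumor; 10% incomplete data or refusal among those invited; prevalence of residual tumor 10–30%, average 20%.

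**The plan's own figures.**
- Normal approximation, one-sided alpha: [1.645·√(0.90·0.10) + 0.842·√(0.95·0.05)]² / 0.05² = 183.3, so 184. This matches.
- Exact binomial at n = 194: the smallest passing count at alpha 0.05 is 182 (93.8%). P(X ≥ 182) is 0.043 at sensitivity 0.90 and 0.824 at 0.95. The protocol does not print the limit of 182; it follows from its inputs.
- 194/0.90 = 215.6, so 216; 216/0.20 = 1080. Both match.

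**(a) Failed biopsies.** Let s be sensitivity over all tumor patients with failures counted as not detected, and f the share of tumor patients with no biopsy. The complete-case value is s/(1 − f). With s = 0.90 and f assumed:

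| f | Complete-case sensitivity | P(X ≥ 182 of 194) |
|---|---|---|
| 0 | 0.900 | 0.043 |
| 1% | 0.90/0.99 = 0.909 | 0.095 |
| 2% | 0.90/0.98 = 0.918 | 0.19 |

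**(b) Unresected patients.** Let v+ and v− be the resection rates in biopsy-positive and biopsy-negative patients. Observed sensitivity is s·v+ / [s·v+ + (1 − s)·v−].

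Tumor status is unknown before resection, so a cancellation rate w = 1 − v− applies to all biopsy-negative patients. At 20% prevalence, s = 0.90 and specificity near 100% (Section 4.4), their share is 0.80 + 0.20·0.10 = 0.82. A loss of L of all participants, all biopsy-negative, therefore means w = L/0.82. With v+ = 1:

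| L | w | Observed sensitivity | P(X ≥ 182 of 194) |
|---|---|---|---|
| 5% | 0.061 | 0.90/(0.90 + 0.0939) = 0.906 | 0.07 |
| 10% | 0.122 | 0.90/(0.90 + 0.0878) = 0.911 | 0.11 |

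The prevalence range changes little. At L = 10%, the biopsy-negative share is 0.91 at 10% prevalence and 0.73 at 30%, and the observed value is 0.910 or 0.9125 (false success 0.10 or 0.12).

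**Direction of (b).** With equal losses, v+ = v− = 0.9: 0.81/(0.81 + 0.09) = 0.90, no bias. With the reverse pattern, v+ = 0.9 and v− = 1: 0.81/(0.81 + 0.10) = 0.890, a slight underestimate.

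**The case against.** Several stronger readings are tempting, and the documents do not support them.

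- **That (b) biases sensitivity upward as a matter of course.** Section 4.2 requires resection to be advised, planned and agreed before entry. Section 8.3.1 offers participation only after the operation has been planned, and Section 8.6 expects withdrawn patients to have it. Biopsies taken during full-thickness resection leave no time for the result to matter. These points make (b) smaller and conditional. They do not exclude it, because patients may leave freely and nothing in the plan would show which pattern occurred.
- **That results are released before surgery because blinding is absent.** Section 8.2, "Randomization, blinding and treatment allocation", is marked not applicable, as expected in a study with no allocation. No section says that results are given to patients or withheld from them. The cancellation item in Section 8.1.3.4 concerns the effect of a complication, not of a negative biopsy.
- **That cancellation could plausibly reach 20–50% of biopsy-negative patients.** These rates would give false-success probabilities of 0.19 to 0.78. But with 82% of participants biopsy-negative, they mean 0.20·0.82 = 16% to 0.50·0.82 = 41% of everyone unresected, against a planned 10% loss that also includes refusals.
- **That an unidentified site always means no biopsy.** Section 8.1.3.4 records the number of biopsies separately. A patient biopsied despite uncertain localization stays in the analysis.
- **That failures must count as negative in the primary analysis.** Section 8.1.1 defines the sensitivity of biopsies, and a missing biopsy gives no negative result on which to omit surgery. Making this primary would also cut power. If biopsies detect 95% when obtained, failures of 2% or 5% give 0.95·0.98 = 0.931 or 0.95·0.95 = 0.9025, and P(X ≥ 182) falls from 0.82 to 0.42 or 0.05.

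Correction methods are often left to an analysis plan. The drop-and-replace rule, however, is stated in the protocol and decides who enters the primary estimate.

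**Conclusion.** The point holds in a limited form. Section 10 removes attempted but failed second looks, which overstates sensitivity relative to counting them as not detected. It also removes unresected patients, which overstates sensitivity only if biopsy-negative patients forgo resection more often than biopsy-positive ones.

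Within the protocol's own loss allowance, the second effect is at most about 1.1 percentage points at 20% prevalence, with false success 0.11 instead of 0.043. That ceiling assigns the entire 10% to biopsy-negative cancellations, although the figure also covers refusals. The first effect needs fewer losses: 1% or 2% failures among tumor patients bring false success to about 0.10 or 0.19.

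All loss rates are assumptions, since the protocol does not split its 10%. The figures also rest on true sensitivity 0.90, the derived limit of 182 of 194 and, for (b), every biopsy-positive patient being resected. The plan should be amended so that the size of these effects can be seen.

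**What to change.** Keep the complete-case estimate as primary if wished, and pre-specify three additions in Section 10:

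1. A table of all patients with an attempted second look, giving reasons for missing biopsies or specimen, with unresected patients shown by biopsy result.
2. A key sensitivity analysis that counts attempted second looks with no biopsy obtained as not detected when the specimen shows tumor.
3. For unresected patients, an analysis corrected for partial verification (Begg-Greenes, or inverse-probability weights), or worst-case bounds.

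Any non-inferiority claim should state whether it survives items 2 and 3. With the primary analysis unchanged, the sample size of 194 stands.

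The cost is new wording in Section 10 and modest extra analysis. Scar finding, number of biopsies, biopsy pathology and surgical data are already collected under Sections 8.1.3.4 to 8.1.3.7. The downside is that the supporting estimates may look less favorable than the headline one.

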10.1 Primary study parameter(s)

As is described in chapter 8.1.1

10.2 Secondary study parameter(s)

As is described in chapter 8.1.2

10.3 Interim analysis

As is described in chapter 8.7.

## **11 Ethical considerations**

### **11.1 Regulation statement**

The study will be conducted according to the principles of the Declaration of Helsinki (version, date, see for the most recent version: [www.wma.net](http://www.wma.net)) and in accordance with the Medical Research Involving Human Subjects Act (WMO)

### **11.2 Recruitment and consent**

After polypectomy, the patient is seen on the outpatient clinic to be informed by the treating physician, usually a gastroenterologist, about the fact that the polyp contained adenocarcinoma, and that it is uncertain whether the resection is complete from an oncological point of view. Staging procedures are arranged and the patient is discussed in a multidisciplinary oncological meeting.

A second visit on the outpatient clinic is planned after the meeting, in order to inform the patient about the results of staging and the outcome of the oncological multidisciplinary meeting. So far, this is the standard of care in patients with this problem.

If additional surgical resection was proposed in the multidisciplinary oncological meeting, and the patient fulfills the inclusion criteria (chapter 4.2), participation in the study is proposed by the treating physician (usually a gastroenterologist).

In case a tattoo needs to be done for laparoscopic surgery, the endoscopic procedure will be planned and the patient will be asked to consent to take biopsies from the polypectomy site. Otherwise, a separate endoscopic procedure needs to be planned as is explained in chapter 8.3.1.

### **11.3 Objection by minors or incapacitated subjects (if applicable)**

Not applicable. Patients who are not able to provide written informed consent are excluded

### **11.4 Benefits and risks assessment, group relatedness**

Participation in the study is in principle of no benefit to the patient. It should be kept in mind, however, that in case a second colonoscopy needs to be done, back-to-back colonoscopy studies have shown the discovery of additional polyps in 10-25% of cases, which implies some benefit in this subgroup, as the removal of these polyps may prevent cancer.

Although not specifically addressed in studies, the risk of taking biopsies from a healed polypectomy wound is considered virtually zero, as is our own experience as well. It is even unnecessary to discontinue systemic anticoagulants such as coumarins or double thrombocyte aggregation inhibition.

The risk of as sigmoidoscopy and colonoscopy are roughly the same and are associated with polypectomy, which can cause perforation and bleeding, both immediately or delayed. In a mixed population of diagnostic and therapeutic colonoscopies, both are approximately one to two in 1000 procedures. The intent of the investigational procedures in this study is only to take biopsies. The risk if the investigational procedure is to our best guess considered very small, less than 1 out of 5000.

The study is specifically related to the group of patients described in the inclusion criteria.

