**Nature and extent of the burden and risks associated with participation and benefit (only applicable for biopsy-part of the study):** Depending on the situation: a): In case a tattoo needs to be done of the polypectomy site before surgery, or an endoscopic full-thickness resection is done, taking biopsies will be of no extra burden; b): In case no endoscopy is indicated before surgery (including TEM / TAMIS), a sigmoidoscopy (lesion distal to the splenic flexure) or occasionally colonoscopy (proximal to the splenic flexure) needs to be arranged for the purpose of this study. A sigmoidoscopy takes 10-20 minutes. Preparation consists of two enemas or flavored polyethylene glycol solution, depending on

NL51461.078.15 / NCT02328664 Scar biopsies after malignant colorectal polypectomy of uncertain radicality

the local protocol. A colonoscopy takes 20-30 minutes. Preparation consists of drinking flavored polyethylene glycol solution, both usually done at home. Notice that the patient has recent experience with colonoscopy. If necessary, both investigations can be arranged under conscious sedation (the rule in colonoscopy), which also implies day-care admission.

The risk of complications of a second endoscopy is estimated < 1:5000. The benefit of a 2nd colonoscopy is the discovery of new polyps in 10-25% of cases.

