## 1 Introduction and rationale

Colorectal carcinoma (CRC) is the second most important cause of cancer mortality in the Netherlands with 15.003 new cases (2014) and 4940 deaths in 2013. Colorectal cancer usually develops from an adenomatous polyp, which is primarily resected via colonoscopy. The number of colonoscopies has dramatically increased with the introduction of population-based screening for colorectal cancer (2014). One or more polyps are roughly found in 1 out of 3 colonoscopies, and may harbor adenocarcinoma in 3-9%. This is sometimes unsuspected: Kudo *et al* reported that 2.8% of benign looking colonic polyps harbor invasive cancer.

Unfortunately, the pathologist is sometimes unable to guarantee a radical endoscopic resection from an oncological point of view. The bowel wall is thin and margins for endoscopic resection are limited to the submucosal space, often less than 1 mm. En-bloc resection is often impossible or too dangerous (perforation). Thus, the majority of endoscopic resection specimens show a tumor-free resection margin < 1 mm or a resection margin that is impossible to evaluate due to piecemeal resection (multiple fragments). For these patients, additional surgery is advised. However, residual tumor at the polypectomy site in surgical rescue specimens is found in only 5 (uncertain radical) to 30% (certainly not radical) of patients.

Affected locoregional lymph nodes are also of concern, even when imaging studies are normal. They are, however, rarely encountered in case of a moderately to well-differentiated adenocarcinoma without risk factors for lymph node metastasis (deep (> 1mm) submucosal invasion, tumor budding, a poorly differentiated histology and/or invasion of lymphatic or blood vessels). If one or more of these risk factors for lymph node metastases are present, metastases can be found in 11-15% of these surgical specimens. In such cases, the decision to additional surgery is made independently of local radicality.

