### 2.2 Secondary Objectives:

[figure not shown]
- 90-day mortality after rescue surgery: the number of patients that died within 91 day after the operation for presumed residual adenocarcinoma
- The sensitivity of biopsies for residual cancer in the bowel wall: the number of patients with endoscopic biopsies containing adenocarcinoma divided by the number of patients with adenocarcinoma in the resected bowel wall (regardless of regional lymph nodes)
- The number of complications (defined according to GCP and the Dutch Association of Gastroenterology) after biopsies from the polypectomy: the number of patients with bleeding or perforation after taking biopsies from the polypectomy scar, requiring at least prolongation of treatment, or admission to hospital, or delay or speeding up rescue surgery. This up until the moment of surgery.
- The sensitivity of global endoscopic assessment of initial polypectomy as well as scar biopsies for residual cancer: the number of patients in whom the endoscopic resection was assessed as incomplete and who also have residual cancer in the surgically resected specimen divided by the total number of patients in whom the endoscopic resection was judged to be incomplete.
- The proportion of patients with residual cancer in the resected specimen if malignancy was unsuspected during the endoscopic polypectomy: the number of patients in whom the malignancy was initially unsuspected during endoscopic polypectomy and who also have residual cancer in the surgical specimen divided by the total number of patients in whom the malignancy was initially unsuspected during endoscopic polypectomy.
- The proportion of patients in whom exclusion criteria apply and the results of surgery / complications of surgery in these patients.

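### For patients having a second full colonoscopy, the stated benefit includes removing new polyps but the stated risk (below 1 in 5000) and the complication endpoint are worded for scar biopsies only

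*Protocol*

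**What the plan says.** Protocol 11.4 makes two statements about a second colonoscopy.

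- **Benefit.** Additional polyps are found in 10-25% of back-to-back colonoscopies, "which implies some benefit in this subgroup, as the removal of these polyps may prevent cancer".
- **Risk.** Complications of sigmoidoscopy and colonoscopy "are associated with polypectomy, which can cause perforation and bleeding, both immediately or delayed". In mixed diagnostic and therapeutic colonoscopy "both are approximately one to two in 1000 procedures". The text then narrows the scope: "The intent of the investigational procedures in this study is only to take biopsies". It concludes: "The risk if the investigational procedure is to our best guess considered very small, less than 1 out of 5000".

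Section 9.2.2 repeats the risk paragraph. The Summary omits the biopsy-only qualifier: "The risk of complications of a second endoscopy is estimated < 1:5000". Its next sentence gives the 10-25% polyp yield as the benefit.

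The secondary complication endpoint in 2.2 counts "the number of patients with bleeding or perforation after taking biopsies from the polypectomy scar", provided the event had a clinical consequence, up to the time of surgery.

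**The concern.** Polyp removal is counted when the benefit is described and left out when the risk is described. Either removal is a consequence of the study colonoscopy, and its harm belongs in the risk figure, or it is not, and the benefit should not be claimed. Putting removal off to a later session does not resolve this, because benefit and harm would move together.

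The issue is sharpest where 8.3.1 has a colonoscopy arranged only for the study. There the ethics committee is weighing the study's own benefit and risk, and the Summary gives it a biopsy-only estimate labelled as the risk of the whole procedure.

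The endpoint has the same scope problem. A summary of complications built on the wording of 2.2 would cover the scar biopsies and could omit harm from the rest of the endoscopy.

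**Working it through.** **1. The protocol's own figure.** The ceiling is 1/5000 = 0.2 per 1000. The protocol presents it as a guess, with no formula or inputs, so it cannot be reproduced. It can only be compared with the other figures given.

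**2. Inputs.**
- Bleeding and perforation in mixed colonoscopy: 1-2 per 1000 (9.2.2, 11.4). The natural reading is 1-2 per 1000 for each, so 2-4 per 1000 together if the two do not overlap. The alternative reading is 1-2 per 1000 for both combined.
- Second colonoscopies with new polyps: 10-25% (Summary, 8.3.1, 11.4).
- For a sensitivity calculation only, from section 1: "One or more polyps are roughly found in 1 out of 3 colonoscopies".

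**3. Formula.** Added risk per second colonoscopy = share with a new polyp removed x complication risk of a session with polyp removal.

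**4. Unscaled result.** The mixed rate is used as the rate for a session with polyp removal. This is cautious, because the protocol links the risk to polypectomy and the mixed population includes procedures without it.

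| Reading of 1-2 per 1000 | Low end | High end | Multiple of 1/5000 |
|---|---|---|---|
| Each (2-4 together) | 0.10 x 0.002 = 0.0002 = 1/5000 | 0.25 x 0.004 = 0.0010 = 1/1000 | 1 to 5 |
| Combined (1-2 together) | 0.10 x 0.001 = 0.0001 = 1/10000 | 0.25 x 0.002 = 0.0005 = 1/2000 | 0.5 to 2.5 |

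These amounts come on top of any risk from the biopsies and sedation. Of the corner values, only 10% with 1 per 1000 falls below the ceiling. At 10% with 2 per 1000 the result equals it, and at 25% with 1 per 1000 it is 1/4000.

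**5. Break-even.** Polyp removal alone uses up the ceiling when its risk per session is 0.0002/0.10 = 1/500 (10% with polyps) or 0.0002/0.25 = 1/1250 (25%).

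**6. Scaled result (assumption).** If all the mixed-population risk fell on the 1 in 3 colonoscopies with polyps, the rate per session would triple:
- each reading: 0.10 x 0.006 = 1/1667 to 0.25 x 0.012 = 1/333, which is 3 to 15 times the ceiling;
- combined reading: 0.10 x 0.003 = 1/3333 to 0.25 x 0.006 = 1/667, which is 1.5 to 7.5 times.

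**7. Averaged over all participants.** The share having a full colonoscopy is not given. On the unscaled each reading, an assumed share of 25% gives 1/20000 to 1/4000, and 50% gives 1/10000 to 1/2000.

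**8. Endpoint against data collection.** Section 2.2 counts bleeding or perforation following scar biopsies. Sedation, which the Summary describes as usual for colonoscopy, can cause harm that is neither. A bleed from another polyp removed in the same session is outside the endpoint if the wording is causal and inside it if the wording only means later in time. Section 8.1.3.4 records bleeding, perforation, intervention, effect on surgery and severity for the second endoscopy, and 9.2.1 records all adverse events whether related or not. No item in 8.1.3.4 records whether another polyp was removed, so an event cannot be assigned to the biopsies or to the removal.

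**The case against.** The strongest reply is that 9.2.2 and 11.4 limit the figure to the investigational procedure and call it a guess. Within that scope the mixed-procedure rates do not contradict it. The protocol does not say that new polyps are removed in the study session, and 11.4 opens by saying that participation in principle brings no benefit. This stands as far as it goes: the 1/5000 is not an arithmetic error for biopsies alone. It does not rescue the Summary, which drops the limit, and it does not explain why removal appears on the benefit side.

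A second reply is that the excess concerns a subgroup. This also stands. The Summary calls a study-only colonoscopy occasional, and others have a sigmoidoscopy or are biopsied at an endoscopy already needed. The Summary draws the line at the splenic flexure and 8.3.1 at the recto-sigmoid, so the size of the subgroup is not settled.

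Four stronger readings might be inferred, and the protocol does not support them.

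- **That the harm goes unmeasured.** Events are captured under 8.1.3.4 and 9.2.1, patients are followed to 92 days after operation (9.2.2), and adverse events after the endoscopies go to the safety committee (9.5). The gap is in the endpoint wording and in attribution.
- **That patients biopsied during endoscopic full-thickness resection dilute the complication rate.** Section 2.2 defines a count with no denominator, and the share of such patients is not given.
- **That the risk is 3 to 15 times too low.** That range needs the 1-in-3 scaling, which carries a polyp rate from one source to complication rates from others.
- **That patients are misinformed at consent.** The patient information is not available, so this cannot be judged.

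**Conclusion.** The point holds for patients having a second full colonoscopy. Benefit and risk cover different procedures, and the Summary applies a biopsy-only ceiling to the whole endoscopy. On the protocol's figures, polyp removal alone accounts for 1 to 5 times the ceiling, or 0.5 to 2.5 times if 1-2 per 1000 is a combined rate.

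These multiples assume that every new polyp found is removed, that the mixed rate applies to those sessions, and, for the first range, that bleeding and perforation do not overlap. Understatement is not shown for participants as a whole.

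The endpoint in 2.2 excludes sedation harm other than bleeding or perforation, and excludes or leaves unclear harm from removing another polyp. The primary endpoint, sample size and stopping rule are unaffected.

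**What to change.** 1. In the Summary, 9.2.2 and 11.4, and in the patient information if it carries the same figure, label the 1/5000 ceiling as applying to biopsies only. Then either give a separate figure for a second colonoscopy in which polyps are removed, with its source and derivation, or remove polyp removal from the stated benefit. Whichever is chosen, the passages must agree on what the study colonoscopy includes.
2. Reword the complication endpoint in 2.2 as any complication of the second endoscopy up to surgery, whichever step caused it.
3. Add one item to 8.1.3.4 recording whether another polyp was removed, so that events can be attributed.

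The cost is a text amendment, a less favourable stated risk or the loss of a claimed benefit, and one form field. No study procedure changes.
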